#### Confidentiality Statement

---

Data and information contained in this document are considered to constitute trade secrets and confidential commercial information, and the legal protections provided to such trade secrets and confidential information are hereby claimed under the applicable provisions of applicable law. No part of this document may be publicly disclosed without the written consent of Philip Morris Products S.A.

---

to nicotine exposure. Spot-urine collection will be performed, and the BoExp levels will be adjusted to creatinine to adjust urinary excretion rates.

This study is designed as an *ad libitum* study without product use restriction in order to mimic as closely as possible “real life” condition.

All patients will be asked to buy their own cigarettes or *HeatSticks*, according to their needs for the study, in order to minimize any changes in their smoking behavior, and to not promote one product over the other.

## 4.2 Appropriateness of Measurements

All dental variables to be measured in this study were selected based on the following criteria: 1) commonly assessed by dentists; 2) acceptability by patients; 3) robustness of the method (*i.e.*, index or evaluation criteria are available to assess improvement of periodontal disease); 4) clinical relevance to support the objectives of the study.

Blinding of the examiners is planned to reduce the potential bias of the periodontal assessments that could be introduced by the smell of tobacco on patients using cigarettes, which is not present on patients using IQOS. Blinding was applied in studies by Preber and Bergstrom [90], Liu and Hwan [46], Rosa et al. [44] and Nair et al. [33]. If the examiner gets unblinded, this will be reported by the Investigator, but the patient will not be discontinued. Because mouth wash may influence the collection of samples, the patients will be instructed not to use mouth wash during the study. Blinding will be ensured by asking the patients to wash their hands before the examination, and the examiners will all wear the same mask, that will mask odors. The patients will also be asked not to drink, eat, chew gum, use mouth rinse or brush their teeth for at least 30 minutes before collection of oral samples, because of the influence it may have on the analytes.

The measurement of PD or CAL can be quite variable, as it depends on 1) the extent to which a probe penetrates into a given pocket (can vary because + line, can vary by more than 0.5 mm 2) the diameter of the probe tip (*e.g.*, WHO probe, Florida probe, Williams SE manual probe) 3) the tine (part of the probe with markings) 4) the probing force used, which is a further major factor influencing probe penetration 5) the angulation of the probe tine to the pocket wall 6) the accuracy or otherwise of markings on the tine, which even in the same batch from a production line can vary by more than 0.5 mm 7) the experience of the examiner 8) the presence of (overhanging) restorations [91]. Intra-examiner reproducibility has nevertheless been shown to be high, with calibration and operator training, rather than operator experience being fundamental for reproducibility [92]. In the oral health component of the National Health and Nutrition Examination Survey (NHANES), cycle 1999–2004, intraclass correlation coefficients for mean loss of periodontal attachment varied from 0.72 to 0.93 and for mean PD from 0.55 to 0.87 [93]. Another study where 3 periodontists were trained and calibrated showed inter-examiner variance from the “reference examiner” for the other 2 of 0.32 and 0.50 mm for PD measurement and 0.56 and 0.52 mm for CAL measurement [32]. In a study involving 18 clinical centers, clinicians were

### Confidentiality Statement

---

Data and information contained in this document are considered to constitute trade secrets and confidential commercial information, and the legal protections provided to such trade secrets and confidential information are hereby claimed under the applicable provisions of applicable law. No part of this document may be publicly disclosed without the written consent of Philip Morris Products S.A.

---

trained and calibrated to measure PD: interexaminer reliability was high, with intraclass coefficients and percent agreement (within 1 mm) values ranging from 0.81 to 0.98 and 87.5% to 98.5%, respectively [94]. To decrease variability in the present study, the same dental probe will be used by all examiners, and a calibration session of all examiners will be organized.

The BoExp measured in this study were selected based on the following criteria: 1) the availability of a validated analytical method; 2) the measure is known to be directly or indirectly affected by the use of tobacco product; 3) the measure is readily reversible after smoking cessation/abstinence; 4) the timeframe of reversibility of measure in the perspective of the study duration; 5) the practicality/acceptability by patients; 6) the robustness of the method (rapid, simple, accurate).

### 4.3 Study Duration

The study duration per patient will be of maximum of up to 31 weeks, including a 1-day visit (V1), up to 2 weeks interval between V1 and V2, followed by a 6-month (the month means 30 days) investigational exposure period, with 1-day visits after 3 and 6 months (V3,  $\pm 7$  days, V4,  $\pm 14$  days at each visit), and a 1-week safety follow-up period. The end of the study for an individual patient will be defined as V4 or the date of early termination plus the 7 days for the safety follow-up period. The end of the entire study is the latest date that an individual patient reaches the end of the study.

## 5 STUDY POPULATION

### 5.1 Selection of Study Population

#### 5.1.1 Inclusion Criteria

At the screening visit (V1), each patient to be enrolled must meet the following criteria:

#### **Study Population and Main Criteria for Inclusion:**

A sufficient number of patients will be enrolled in order to randomize at least 172 patients meeting the following main inclusion criteria:

1. Patient is Japanese.
2. ICF has been signed.
3. Patient is aged  $\geq 30$  years old.
4. Patient has smoked on average at least 10 commercially available cigarettes per day (no brand restriction) for at least 5 years prior to V1, based on self-reporting. Smoking status will be verified based on a urinary cotinine test (*i.e.*, cotinine  $\geq 200$  ng/mL).
5. Patient has at least 15 natural teeth (refer to Definition of Terms), excluding the teeth which need to be extracted or whose mobility grade is  $\geq 3$ .
6. Patient has generalized chronic periodontitis (*i.e.*, more than 30% of diseased teeth with a PD  $\geq 4$  mm), considering only teeth that do not need to be extracted or whose mobility grade is  $< 3$ .
7. Patient does not intend to quit smoking during the study.
8. Patient is ready to comply with study procedures and to use the product he/she is allocated to for the duration of the study.

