#### Confidentiality Statement

---

Data and information contained in this document are considered to constitute trade secrets and confidential commercial information, and the legal protections provided to such trade secrets and confidential information are hereby claimed under the applicable provisions of applicable law. No part of this document may be publicly disclosed without the written consent of Philip Morris Products S.A.

---

controlled temperature range (far lower temperatures than cigarette) rather than burning it. IQOS replicates the ritual of smoking but without combustion. [60, 61].

IQOS is composed of the Holder and of dedicated *HeatSticks*. In this document, unless otherwise specified, IQOS refers to the device with *HeatSticks*. No other tobacco sticks should be used with the device. A Charger allows to recharge the Holder after each use. Unlike cigarettes, the *HeatSticks* do not burn down during their consumption and their lengths remain constant after use. IQOS has been commercialized in Japan since November 2014. With this product, the heating of the tobacco is maintained below 350°C, a temperature much lower than what is observed for cigarette, which can reach 900°C.

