### 3 STUDY OBJECTIVES

#### 3.1 Primary Objective and Endpoint

The primary objective of this study is:

To demonstrate the effect of switching to IQOS use compared to continued cigarette smoking on the response of PD to mechanical periodontal therapy.

Endpoint (6 months):

- Mean PD reduction in all sites with initial PD  $\geq 4$  mm after mechanical periodontal therapy.

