The choice of the primary and secondary objectives are based as a selection of 1) the most published assessment, *i.e.*, reduction of PD, which has been shown to occur rather rapidly after mechanical therapy (*i.e.*, within 3 to 6 months) and is more representative of the overall inflammation, 2) the most clinically relevant endpoint, *i.e.*, CAL change, which is more representative of tissue destruction, and is thus determinant in the increased risk of tooth loss. Data on CAL change in smokers vs non-smokers or quitters, are, however, sparser than data on PD. The assessment of both parameters as primary and secondary endpoint will thus provide evidence on both the effect of IQOS on inflammation status and on tissue repair and will provide information about the modification of the healing profile related to switching to IQOS.

The limitation of use of antibiotics before and during the study is largely driven by the differential effect that those may have on healing after mechanical periodontal therapy [85], but also, to a slighter extent, because they will affect the microbial oral environment of the patients. Similarly, use of steroidal or non-steroidal anti-inflammatory drugs may affect healing [86, 87], bisphosphonates, which have been shown to be effective in periodontitis management through inhibition of the alveolar bone resorption, should be considered with care during the study because of a potential risk of osteonecrosis of the jaw [88]. Anti-coagulants should also be considered with care because of the risk of bleeding [89].

BoExp to NEQ, nicotine-derived nitrosamine ketone (NNK) (total NNAL) and acrylonitrile (CEMA) will serve as indicators of overall exposure of the patients throughout the study. These markers have relatively long half-lives, and should provide a good estimate of the exposure, even if the patient comes early in the morning for his/her visit. Because nicotine is expected to be delivered with IQOS at levels comparable to cigarettes, levels of NEQ are not expected to be lower in IQOS users than cigarette users, but it will serve as an overall estimate of exposure

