## 6.3 Method for Assigning Patients to Study Arms

After all assessments of V1 have been completed, patients will be randomized to 1 of the 2 study arms; continued cigarette smoking or IQOS use. Patients will be informed about their study arm allocation at V2. Randomization will be done through the Interactive Web and Voice Response System (IXRS) at any time during the visit. Patients will be randomized in one of the two study arms, IQOS arm:cigarette arm in a 1:1 ratio using a stratified randomization (based on daily cigarette consumption over the month (30 days) prior to V1 (10-19 cigarettes/day vs. >19 cigarettes/day), and disease severity (< 5 mm PD vs.  $\geq$  5 mm PD) in smokers with generalized chronic periodontitis. Disease severity is based on the tooth site having the most severe condition of PD [78]. In each arm, a quota will be applied to ensure that patients with PD  $\geq$  5 mm represent at least 50% of the randomized patients. Arm assignment for patients with PD < 5 mm will be capped at n = 80, after which enrollment of patients with PD < 5 mm will be stopped. Patients with PD < 5 mm already enrolled but not randomized may be discontinued in order to ensure that randomization quota are met. Enrollment of patients with PD  $\geq$  5 mm will continue until 172 patients are randomized. At this stage, patients' enrollment will be stopped and patients already enrolled but not randomized may be discontinued. In case patients are discontinued after V1, they will be referred to their dentist/general practitioner and will receive financial compensation for the

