#### 7.3.2 Questions on Smoking History/Habits and Intention to Quit Smoking

Patients will be questioned for their smoking history and self-reported current tobacco and nicotine containing tobacco product use over the past month at V1. The patient will also be asked if he/she is planning to quit smoking during the study. This information will be used to assess their eligibility for the study.

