#### 12.1.1 Stratification Criteria

For the primary analysis of PD, the following stratification criteria will be used:

1. Daily cigarette consumption over the month (30 days) prior to V1 (10-19 cigarettes/day vs. >19 cigarettes/day)
2. Disease severity in smokers with generalized chronic periodontitis (< 5 mm vs.  $\geq$  5 mm PD).

In each arm, a quota should be applied to ensure that patients with PD  $\geq$  5 mm represent at least 50% of the randomized patients (section 6.3).

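### Patients already part-switched to HeatSticks at V1 can enter, and the V1 product use that would show this is collected but left out of the by-use primary model and the baseline tables

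*Protocol*

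**What the plan says.** The primary objective (Protocol 3.1) is "To demonstrate the effect of switching to IQOS use compared to continued cigarette smoking on the response of PD to mechanical periodontal therapy".

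Entry rests on inclusion criterion 4 (Protocol 5.1.1, repeated in SAP 4.2.1): "Patient has smoked on average at least 10 commercially available cigarettes per day (no brand restriction) for at least 5 years prior to V1". It adds "Smoking status will be verified based on a urinary cotinine test" at 200 ng/mL or more. The protocol's explanation of terms does not count HeatSticks as cigarettes. None of the 8 inclusion and 15 exclusion criteria mentions HeatSticks, e-cigarettes or nicotine replacement.

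Protocol 7.3.2 has patients report past-month tobacco and nicotine product use at V1 and states: "This information will be used to assess their eligibility for the study". No criterion says how. Protocol 7.5.7 and the schedule of events confirm the V1 questionnaire.

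Randomization is stratified on "daily cigarette consumption over the month (30 days) prior to V1 (10-19 cigarettes/day vs. >19 cigarettes/day") (Protocol 6.3, with the same cut-points in 12.1.1 and SAP 4.3.1).

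The primary analysis (SAP 8.1 and 9.5.1.1) uses the As Exposed Set, grouped as IQOS user, cigarette user or dual user. SAP 5.2.1 builds these groups from post-randomization questionnaires only.

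**The concern.** The trial asks what happens when a smoker switches, so each patient's starting point matters. Protocol 2.1 notes that "IQOS has been commercialized in Japan since November 2014", almost three years before protocol version 2.0 of 05 September 2017. Some smokers presenting at V1 could therefore already be using it.

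Two consequences are plausible. Prior HeatStick use may influence whether a patient ends up as an IQOS, dual or cigarette user. It may also be related to the response: someone who cut down on cigarettes before V1 has made part of the change before baseline pocket depth is measured, and may differ in other habits. A variable linked to both group and outcome is a confounder. The primary groups are formed by behavior after randomization, so only the model can deal with it, and the model does not contain it.

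There is a smaller, separate question about whether the strata cover everyone who is eligible.

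**Working it through.** The main point is a reading of the text; arithmetic enters only for the stratum question.

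**Plan's own figure.** Protocol 12.2 needs 64 evaluable patients per arm. Allowing 25% for drop-out and product switching gives 64 / (1 - 0.25) = 85.3, so 86 per arm and 2 x 86 = 172. This reproduces, and nothing below changes it.

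**Can the cotinine test screen out HeatStick users?** No. Protocol 4.1 says "Because nicotine is expected to be delivered with IQOS at levels comparable to cigarettes", so a positive test shows nicotine intake, not its source.

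**Does the primary model hold V1 HeatStick use?** The 13 terms in SAP 9.5.1.1 sort as follows:
- cigarettes before randomization: term 1, and term 8 (its interaction with product use);
- product use after randomization: terms 5, 6 and 7;
- disease and dental treatment: terms 2, 3 and 9 to 13;
- visit: term 4.

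None records non-cigarette use at V1. Take two patients who each smoke 12 cigarettes a day at V1, one of whom also uses 10 HeatSticks. They share the 10-19 stratum and the same value of term 1, so these variables do not separate them.

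**Do the planned outputs show it?** In SAP 9.3, the demographics table carries the cigarette stratum and the smoking-history table lists cigarettes only. In SAP 9.4, the product-use table is for the overall period and the listing covers months 1 to 6 and overall; neither shows V1. Baseline urinary biomarkers are summarized by use category (SAP 9.5.2.1), but they do not identify the product and are not in the primary model.

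**Do the strata cover all eligible patients?** The stratification variable is "Daily cigarette consumption over the month (30 days) prior to V1 (10-19 cigarettes/day vs. >19 cigarettes/day"), with no category below 10. Suppose criterion 4 is a 5-year (60-month) average:
- 20 a day for 48 months, then 5 a day for 12: (20 x 48 + 5 x 12) / 60 = 1020 / 60 = 17.0 a day. Eligible, but no stratum.
- 9 a day for the last 6 months: the earlier 54 months need only (10 x 60 - 9 x 6) / 54 = 546 / 54 = 10.11 a day to qualify. Again no stratum.

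If criterion 4 means at least 10 a day sustained up to V1, the gap closes.

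**The case against.** **A check exists.** Protocol 7.3.2 brings V1 product use into eligibility, exclusions 1 and 3 leave room for investigator judgment, and inclusion 8 requires readiness to use the allocated product. This stands in part: what is missing is a written threshold. The general provisions do not address current HeatStick use, and a current dual user could satisfy them.

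**Mixed users may be wanted.** Use is ad libitum to resemble ordinary life (Protocol 4.1), and dual use is expected (Protocol 12.3). This stands. Excluding HeatStick users is a sponsor design choice, not a correction.

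**The analysis copes in part.** Actual use defines the groups, patients in the other-products category are left out of non-safety analyses (SAP 8), V1 cigarette consumption is in the model, and SAP 9.5.1.1 allows further covariates if judged necessary. But classifying later use does not adjust for earlier use, and an open permission to add terms is not pre-specification.

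**The stratum gap depends on a reading.** SAP 9.3 lists both a 5-year cigarettes-per-day figure and smoking for at least the past 5 consecutive years. Protocol 4.1 explains the 5-year minimum as keeping long-term smokers who paused. That fits an average but does not settle the matter.

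**Stronger readings.** A reader might infer that part-switched patients did enter in number, or that the 0.25 mm effect is diluted and power lost. The documents support neither. They give no prevalence, and market availability does not supply one. A by-arm dilution figure would concern the Full Analysis Set, which is supportive. It would also assume that controls keep using HeatSticks for 6 months despite the instruction to use only their assigned product. Any loss to the dual-user group may already sit within the 25% allowance.

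**Conclusion.** The point holds as a gap in confounder control and reporting. Part-switched patients can enter, their V1 use is recorded, and the plan neither adjusts for it nor tabulates it in a primary comparison that randomization does not protect. The effect on the estimate cannot be sized from the documents, and its direction is unknown, so no millimeter or power figure is attached. If few patients used HeatSticks at V1, the effect would be small, and the proposed table would show this.

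The conclusion rests on the listed criteria and outputs being complete, and on prior use being plausibly related to both later use category and response. Adjustment would reduce one source of confounding; it would not make the by-use contrast a randomized one.

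The stratum mismatch is conditional on the 5-year-average reading of criterion 4.

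**What to change.** In the SAP, before the statisticians are unblinded:

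1. In 9.5.1.1, add V1 past-month HeatStick use, and other non-cigarette product use, as a fixed baseline covariate with its coding stated in advance. Exempt it explicitly from backward selection. The text gives the droppable terms once as 8-12 and once as 7-14, so a new term numbered 14 could be dropped under the second range.
2. Add a sensitivity analysis of the primary endpoint restricted to patients who used only cigarettes at V1.
3. In 9.3, tabulate V1 HeatStick and other-product use by randomized arm and by product-use category.

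To align criterion 4 with the strata, either label the lower stratum as 19 or fewer cigarettes a day in the analysis, or state a past-30-day minimum in criterion 4 that matches the lower bound. Also state how the V1 report under Protocol 7.3.2 decides eligibility.

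The SAP changes use data already collected and leave the sample size at 172. They cost one more model term (two if other products are coded separately), one more run and one table. A past-30-day minimum would need a protocol change and could lose some recruits; relabeling the stratum would not.

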#### 5.1.2 Exclusion Criteria

Patients who meet any of the following exclusion criteria must not be enrolled into the study.

#### **Criteria for Exclusion:**

1. Patient has self-reported history of diagnosed systemic diseases (*e.g.*, stroke or acute cardiovascular event within the last 5 years, diabetes, active cancer), or any other conditions that in the opinion of the Investigator would jeopardize the safety of the participant or affect the validity of the study results.

#### **Confidentiality Statement**

---

Data and information contained in this document are considered to constitute trade secrets and confidential commercial information, and the legal protections provided to such trade secrets and confidential information are hereby claimed under the applicable provisions of applicable law. No part of this document may be publicly disclosed without the written consent of Philip Morris Products S.A.

---

2. Patient is legally incompetent, physically or mentally incapable of giving consent (*e.g.*, emergency situation, under guardianship, in a social or psychiatric institution, prisoner or involuntarily incarcerated).
3. As per the Investigator's judgment, patient cannot participate in the study for any reason (*e.g.*, medical, psychiatric and/or social reason).
4. As per the Investigator's or designee's judgment, patient has medical conditions which require or will require in the course of the study, a medical intervention (*e.g.*, start of treatment, surgery, hospitalization) which may interfere with the study participation and/or study results.
5. Patient has orthodontic appliances.
6. Patient received root planing therapy within the 6 months prior to V1.
7. Patient received surgical periodontal therapy within 3 years prior to V1.
8. Patient has identifiable premalignant changes of the oral mucosa at V1.
9. Patient was treated within the 3 months prior to V1 with systemic antibiotics or was treated with topical antibiotics applied in the mouth.
10. Continuous systemic use of steroidal or non-steroidal anti-inflammatory drugs for more than 20 days during the past 30-day period (except for low dose aspirin, *i.e.*,  $\leq 300$  mg *e.g.*, for prevention of thrombus/embolus in angina pectoris, myocardial infarction, transient ischemic cerebrovascular accidents, bypass operations).
11. Patient has been previously screened or enrolled in this study.
12. Female patients who are pregnant, breast-feeding, or planning a pregnancy within the course of the study.
13. Patient is a current or former employee of the tobacco industry or their first-degree relatives (parent and child).
14. Patient is an employee of the investigational site or any other parties involved in the study or their first-degree relatives (parent and child).
15. Patient has participated in a clinical study within 3 months prior V1.

